4.9 INTERIM ANALYSES

Interim PK analyses will take place for each of the individual age cohorts (<6 years and 6-12 years) once evaluable PK data are available for a minimum of 6 participants in each the cohort.

An interim safety, PK and efficacy analysis will be performed after 12 participants are enrolled in the older age cohort (6-12 years). The PK analysis will be conducted once each of the 12 participants from the older age cohort complete the first dose of BIVV001; the safety and efficacy analysis will be conducted once the12 participants from the older age cohort have reached 25 EDs to BIVV001.

In addition, for the purposes of regulatory submission, an interim analysis of key safety data, PK data and selected efficacy data for this study will be performed when the pivotal adult/adolescent study EFC16293 is completed.

5 SUPPORTING DOCUMENTATION

5.1 APPENDIX 1 LIST OF ABBREVIATIONS

ED:	exposure day
SAP:	statistical analysis plan

5.2 APPENDIX 2 DEMOGRAPHICS AND BASELINE CHARACTERISTICS, PRIOR OR CONCOMITANT MEDICATIONS

Demographic characteristics

Demographic variables include sex, date of birth (year of birth only), height, weight, body mass index (BMI), race, ethnicity and geographic location.

Demographic characteristics will be summarized by age cohort, including the surgery subgroup, and overall for the FAS using descriptive statistics.

Hemophilia history

The following hemophilia history variables will be summarized by age cohort, including the surgery subgroup, and overall for the FAS using descriptive statistics:

- Age at diagnosis of severe hemophilia (years)
- Family inhibitor history (Yes, No)
- Blood type (A, B, AB, O)
- Rh factor (Positive, Negative)
- Lowest documented historical FVIII level (<1%, $\ge1\%$)
- FVIII genotype (Intron 22 inversion, Intro 1 inversion, Frameshift, Missense, Nonsense, Other mutation, Unknown)
- HIV status (Positive, Negative, Unknown)
- Hepatitis B (HBV) status (Positive, Negative, Unknown)
- Hepatitis C (HCV) status (Positive, Negative, Unknown)
- Vaccination history in past 12 months (Yes, No, and if Yes, how many)
- Types of FVIII products previously administered (FVIII plasma derived, FVIII recombinant, FVIII cryoprecipitate, Non FVIII product)
- Age at start of first prophylaxis regimen
- Number of prior exposure days to FVIII ($<50, 50-<100, 100-<150 \text{ and } \ge 150; <150, \ge 150$)

Statistical Analysis Plan BIVV001-EFC16295

- Number of bleeds in the past 12 months
- Number of joint bleeds in the past 12 months
- Number of spontaneous joint bleeds in the past 12 months
- Number of traumatic joint bleeds in the past 12 months
- Number of target joint at baseline

Medical and surgical history

Medical (or surgical) history will be collected at screening and will be coded using the version of Medical Dictionary for Regulatory Activities (MedDRA) in effect at Sanofi at the time of database lock.

The number and percentage of participants with any medical and surgical history will be summarized for each body system by age cohort, including the surgery subgroup, and overall using the Safety Analysis Set. A participant will be counted only once if the participant reported one or more occurrences of the same body system.

Prior or concomitant medications

All medications taken in the 30 days prior to the time the participant enrolls in the study and until the Safety Follow Up Call or Visit are to be reported on the eCRF.

Medications will be identified as being prior and/or concomitant based on the start and stop dates compared to the first dose of study drug. Prior medications are those taken before the first dose of study drug. Concomitant medications are those administered during or after the first dose of study drug. A medication that started prior to the first dose of study drug and was ongoing during and/or after the first dose of study drug will be classified as both prior and concomitant.

No imputation of medication start/end dates will be performed. If the start/end date is missing or partial, the corresponding study day will be left blank. However, inferences will be made from the partial and missing dates to classify the medications as prior and/or concomitant as follows.

If a concomitant medication start day is missing then the medication will be assumed to be both a prior and a concomitant medication unless the start month and/or year or medication stop date can be used to determine if a medication is concomitant or prior, as follows:

- If the medication start day is missing, but the month and year precede the month and year of the first treatment and the medication stop date is before the date of first treatment, then the medication will be classified as prior only.
- If the medication start month is missing, but the year precedes the year of first treatment and the medication stop date is before the date of first treatment, then the medication will be classified as prior only.
- If the medication start day is missing and the month and/or year are on or after the month and year of the first treatment, then the medication will be classified as concomitant only.

All medications will be coded using the World Health Organization-Drug Dictionary (WHO-DD) using the version in effect at Sanofi at the time of database lock.

Separate summaries will be provided for prior and concomitant medications. Prior and concomitant medications will be presented by age cohort and overall for the Safety Analysis Set. Summaries will be based on the number and percentage of participants taking medications by WHO-DD standardized medication text. Within each WHO-DD standardized medication text a participant will be counted once even if he/she reported taking the medication more than once.

Concomitant medications taken for hemophilia-related pain

Concomitant medications taken for hemophilia-related pain will be summarized by age cohort and overall for the Safety Analysis Set. Summaries will be based on the number and percentage of participants taking pain medications by class (acetaminophen/paracetamol, NSAIDs, opioids, other).

In addition, the number of days pain medication was used for hemophilia-related pain in the past 2 weeks will be summarized categorically (0 [None], 1-3, 4-7, 8-14) for each study visit by age cohort and overall.

5.3 APPENDIX 3 DATA HANDLING CONVENTIONS

Electronic Patient Diary (ePD) Data

Participant recorded diary data will be handled taking into consideration previous audit findings and industry standards to control changes to participant reported data. Only changes defined as not requiring participant confirmation and that are supported by site source documentation will be allowed.

The following programming algorithms are allowable to address record consolidation and true duplicate removal.

1) Record consolidation:

When a dose requires more than one vial and these vials are erroneously recorded in the ePD/eCRF as separate injections, albeit within a short time window, the change to consolidate these multiple records into one record is called single vial consolidation. The programming algorithm to identify and consolidate the records is as follows:

- Identify all injection records within 60 minutes of one another where the variables (injection date/times, lot numbers, number of vials, and vials strength in nominal IU) are not exactly the same on each record. There are four scenarios:
 - Date and time of injections are not exactly same, and lot numbers, number of vials, and vials strength in nominal IU are not the same.
 - Date and time of injections are not exactly same, but lot numbers, number of vials, and vials strength in nominal IU are the same.

- Date and time of injections are exactly same, but lot numbers, number of vials, and vials strength in nominal IU are not the same.
- Date and time of injections are exactly same, and lot numbers, number of vials, and vials strength in nominal IU are the same and these duplicates occurred for reasons which cannot be attributed to administrative issues as specified below
- Consolidate injections as follows:
 - Record with earliest injection date/time retained with corresponding contextual information
 - Combine/sum values related to the dose (eg, lot numbers, number of vials, volume injected, nominal and actual dose) into the single retained record

If injections identified with the above algorithm have distinctly different reasons (eg, one injection is recorded as bleeding or surgery and another is recorded as prophylaxis, or OTHER), then the records should NOT be consolidated. However, if one record has reason or bleed information missing, then consolidation can be performed.

2) True duplicates removal:

When injections are identified in the ePD with exactly the same date/times, bleed information if applicable (type, location, and sublocation), lot numbers, number of vials, and vials strength in nominal IU, these may have resulted due to administrative issues and are therefore true duplicates. There are three types of administrative issues as follows:

- Technical transmission issue
- Entry of same record into 2 different devices
- Records duplicated in ePD and eCRF which remain despite attempts to correct the data via the query process

The programming algorithm to identify and delete the duplicates is as follows:

- Identify all injections that have exactly the same date/times, reasons for injection, bleed information (if applicable), lot numbers, number of vials, and vials strength in nominal IU
- Remove the duplicates and keep a single record

As with single vial consolidation, if injections identified as duplicates have distinctly different reasons (eg, one injection is recorded as bleeding or surgery and another is recorded as prophylaxis or OTHER), then these cannot be considered duplicates and removed. However, if one reason is missing, then they can be considered duplicates and removed.

Algorithm for determining analysis visit windows for PRO and HJHS observations

A scheduled measurement will be used if it is available. Otherwise, the following analysis window will decide how the unscheduled and EOS/ET visits will be used in the analyses of PRO and HJHS variables.

A measurement (unscheduled or EOS/ET) will be used if it is available and measurement date is within the analysis window.

After applying these time windows, if multiple assessments are associated to the same time point, the closest from the targeted study day will be used. If the difference is a tie, the value after the targeted study day will be used. If multiple valid values exist within a same day, then the first value of the day will be selected.

Scheduled visit post		Derived Window in study days		
baseline	Target study day	Lower bound	Upper bound	
Baseline	1	-INF	1(7 for HJHS)	
Week 26	182	2 (8 for HJHS)	272	
Week 52	364	273	-	

Table 6 - Analyses window definition

Handling of adverse events with missing or partial date/time of onset

No imputation of adverse event onset/end dates will be performed. If the onset/end date is missing or partial, the corresponding study day will be left blank. However, inferences will be made from the partial and missing dates to classify the adverse events as treatment-emergent or not as follows:

- If the onset day of an adverse event is missing and the onset month and year of the AE are either the same as or later than the month and year of the first treatment, the AE will be considered a TEAE.
- If the onset day of an adverse event is missing and the onset month and year of the AE precede the month and year of the first treatment, the AE will not be considered a TEAE.
- If the onset month of an adverse event is missing and the onset year of the AE is either the same as or later than the year of first treatment, the AE will be considered a TEAE.
- If the onset month of an adverse event is missing and the onset year of the AE precedes the year of first treatment, the AE will not be considered a TEAE.
- If the onset day, month, and year of an adverse event are missing, the AE will be considered a TEAE.
- If start date is partial but the stop date can be determined to be before the start of the first dose of study drug, then the AE will not be considered a TEAE.

Handling of adverse events with missing relationship to investigational product

If the assessment of relationship to study drug is missing, the event will be counted as "related" in the frequency tables of treatment-emergent adverse events by relationship to study drug.

Handling of adverse events with missing severity

If the assessment of severity is missing, the event will be counted as "severe" in the frequency tables of treatment-emergent adverse events by severity.

Unscheduled visits

Unscheduled visit measurements of laboratory data and vital signs will not be included in the byvisit summaries but will be used for computation of baseline, maximum or minimum on-treatment values, and PCSAs.

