4.4.1 Annualized bleeding rate (ABR)

4.4.1.1 Definition of endpoint

Data for bleeding events will be collected by each participant via an ePD or, in the case of bleeds occurring and/or treated at the study site, on the eCRF and will include type of bleed, location of bleed, and treatment dates, if applicable. This information will be used to derive efficacy endpoints on bleeding.

During the course of the study, the Investigator is given the opportunity to disagree with the classification of bleeding episode as given by the caregiver, and the caregiver is subsequently given the opportunity to agree or disagree with the reclassification (spontaneous, traumatic, or not a bleed). If the caregiver agrees with the Investigator's assessment, then all analyses of bleeding will be based on the Investigator's determination of the bleeding type, whether or not the change was made to the participant's records.

Bleeding episodes of an unknown type will be included in the determination of the annualized bleeding rate and in summaries based on bleeding episodes but, unless specified otherwise, will not be included in summary tables where endpoints are summarized by type of bleed.

Definition of a bleeding episode (based on treated bleeds)

All primary analyses of bleeding endpoints will be based on treated bleeds consistent with ISTH criteria (1) using the following standardized definition:

In the analysis of treated bleeds, a bleeding episode starts from the first sign of bleeding and ends no more than 72 hours after the last injection to treat the bleed, within which any subsequent bleeding at the same location, injections \leq 72 hours apart, are considered the same bleeding episode. Multiple bleeding locations treated with a single injection will also be considered a single bleeding episode. Any injection to treat the bleed, taken >72 hours after the preceding one, will be considered the first injection to treat a new bleeding episode in the same location. Any subsequent bleeding or injection at a different location will be considered a separate bleeding episode, regardless of the time from the last injection.

Annualized bleeding rate

The ABR for each individual participant is calculated using the following formula:

$$ABR = \frac{\text{Number of treated bleeding episodes during the efficacy period}}{\text{Total number of days during the efficacy period}} \times 365.25$$

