4.4.10 Annualized joint bleeding rate

The annualized joint bleeding rate (AJBR) will be summarized descriptively by age cohort and overall as described in Section 4.4.1.

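### The diary record-consolidation rule in SAP 5.3 has no express check on bleed location, so a joint site logged second can be lost from AJBR and other location-specific counts

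*SAP*

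**What the plan says.** SAP 5.3 (Appendix 3) has two diary-cleaning algorithms.

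- **Item 1, record consolidation.** It is meant for one dose that needed several vials, where the vials were wrongly entered as separate injections. The programmer is to "Identify all injection records within 60 minutes of one another where the variables (injection date/times, lot numbers, number of vials, and vials strength" [IU]) are not all alike. Four scenarios follow. The last covers records alike on all of these variables where the duplication has no administrative cause. For the merged result the rule is "Record with earliest injection date/time retained with corresponding contextual information", and the dose fields are added up.
- **Limits on item 1.** "If injections identified with the above algorithm have distinctly different reasons", they stay apart; the example contrasts bleeding or surgery with prophylaxis or another reason. Then: "However, if one record has reason or bleed information missing, then consolidation can be performed". The appendix opens by allowing only diary changes that site source documentation supports.
- **Item 2, true duplicates.** Here the records must also agree on "bleed information if applicable (type, location, and sublocation").

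SAP 4.4.1.1 defines the treated episode. On one side: "Any subsequent bleeding or injection at a different location will be considered a separate bleeding episode, regardless of the time from the last injection". On the other: "Multiple bleeding locations treated with a single injection will also be considered a single bleeding episode".

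SAP 4.4.10 states: "The annualized joint bleeding rate (AJBR) will be summarized descriptively by age cohort and overall", by the method of 4.4.1. SAP 4.4.2 summarises ABR, and the percentage of participants with a bleed, by location. SAP 4.4.11 calls a target joint resolved when at most two bleeds occur into it over 12 months.

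**The concern.** Item 2 compares location and item 1 does not. Two complete bleed records that name different sites can share a reason, lie within 60 minutes of each other, and so meet item 1 as written. Only the retained record's context survives, and nothing carries the other site forward.

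For AJBR the error can go only one way: merging can remove a recorded joint site but cannot create one. The endpoints exposed are AJBR, ABR by location, the percentage of children with a joint bleed, and target-joint resolution. All are secondary and descriptive. Total treated ABR is exposed only if the two records were truly separate injections.

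**Working it through.** The plan states no figure on this point, so there is nothing to reproduce. The check is a literal trace of the rule, followed by the SAP's own rate formula.

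**1. Does the reason bar protect location?** Item 1 names reason and bleed information as separate things, and item 2 does the same. SAP 4.7.1.1 lists the reasons for injection as prophylactic regimen, spontaneous bleed, traumatic bleed, follow-up, surgical or other. On that coding, a spontaneous and a traumatic bleed have different reasons and could be kept apart. Two spontaneous bleeds at different sites share one reason, so the bar does not reach them.

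**2. Trace (illustrative records).** Record 1: muscle bleed, 0 min, 1000 IU. Record 2: left-knee bleed, 30 min, 1000 IU. Both have the reason bleed.

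- Item 1 read literally: one record, muscle, 2000 IU. The knee is gone.
- With a location check added: two records, muscle 1000 IU and left knee 1000 IU.
- Order reversed, literal reading: one record, left knee. The muscle site is lost and AJBR is unaffected.
- Record 2 entered as prophylaxis: not merged.

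**3. Rates for that child.** SAP 4.4.1.1: count / days in efficacy period × 365.25. Assume 364 days (52 × 7).

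| | Treated ABR | AJBR |
|---|---|---|
| Literal item 1 | 1/364 × 365.25 = 1.003 | 0 |
| Records kept apart | 2/364 × 365.25 = 2.007 | 1/364 × 365.25 = 1.003 |

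The AJBR loss is 1.023 over 357 days (364 less a 7-day PK period) and 2.007 over 182 days. If the two records were in fact one dose, the treated ABR of 1.003 is what 4.4.1.1 prescribes, and only the AJBR is at issue.

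**4. Cohort mean, one lost joint bleed.** 365.25/364/50 = 0.0201; 365.25/364/65 = 0.0154. The divisors are the planned minimum of 50 completers and the planned enrolment of about 65.

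**5. Target joint.** Three bleeds exceed the limit of two, so the joint is not resolved. Two bleeds meet it, so it is resolved. One relabelled bleed can cross that line, but only in a joint with exactly three.

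**6. Tied times.** If two records carry the same date and time, neither is earliest, so the retained site is undefined. If lots, vials and strength also match and only the site differs, item 2 does not apply because the bleed information differs. If the fourth scenario of item 1 is then used, the dose is summed: one 50 IU/kg treatment entered once per site would be scored as 100 IU/kg.

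**The case against.** There is a fair case that the rule is safer than a literal trace suggests.

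- The sentence allowing a merge when bleed information is missing would have little purpose if conflicting bleed information did not matter. This stands: the text is ambiguous, and a reader who takes it as a definite instruction to merge conflicting sites goes further than it supports. But the sentence gives no instruction for the conflicting case, so two programmers could defensibly do different things.
- The rule is aimed at one dose split over vials, and diary changes need site source documentation. Both narrow the exposure. Neither removes it: the algorithm contains no documentation step, and protocol 8.1.2 makes the diary itself the primary source for bleeding episodes. A single multi-vial dose can still be entered against two sites.
- For a single dose, one episode is the correct count under 4.4.1.1. This stands. A reader might infer that total treated ABR is understated whenever records merge; that holds only for separate injections. It also shows that 4.4.1.1 and 4.4.10 leave open where a multi-site episode counts.
- The doubled dose in step 6 assumes one diary entry per site, which the documents do not establish, and it is arguable whether such records count as the duplicates the fourth scenario has in mind. It is a gap to close, not a demonstrated error.
- Nothing in the documents says how often such pairs occur. If someone assumes that 2–10% of joint bleeds are logged second in a pair, an AJBR understated by 2–10% merely restates the assumption.

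**Conclusion.** The concern holds in a limited form. SAP 5.3 item 1 has no express location check. Read literally, it can drop a recorded joint site from the location-specific endpoints, and for truly separate injections it conflicts with the different-location clause of 4.4.1.1. That is more than missing detail, because the algorithm is stated and can be run as written.

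Per event, one lost joint bleed lowers that child's AJBR by 1.003 and mean AJBR by about 0.015–0.020, assuming a 364-day efficacy period and 50 to 65 children. It could also change one target joint's status. The trial-level effect cannot be estimated from the documents. A reader might conclude that AJBR is materially biased, or that the second site is always lost; the documents support neither.

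**What to change.** Amend SAP 5.3 item 1 before database lock:

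1. Records with different non-missing bleed location or sublocation are not consolidated unless site source documentation confirms a single dose.
2. If a single dose is confirmed, keep every recorded location on the retained record. Count one episode in total ABR, as 4.4.1.1 requires, and count each recorded location in AJBR, ABR by location and target-joint bleeds.
3. If date and time, lots, vials and strength are identical and only the location differs, do not sum the dose unless source documentation shows that two doses or separate vials were given.

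Merging the doses of all near-simultaneous bleed records and simply keeping both sites would not do, because it would join real separate injections that 4.4.1.1 counts as separate episodes.

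The cost is a few sentences and a small programming change. Location-specific rates may add up to more than total ABR, which needs a table footnote, and AJBR may be slightly less favourable.

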A bleeding episode is counted in the analysis if it was treated with BIVV001. All types of bleeding episodes (spontaneous, traumatic, and type unknown) will be included in determining the annualized number.

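### Merging split vial records can keep a blank reason from the earlier record, so a recorded treated bleed may drop out of the ABR

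*SAP*

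**What the plan says.** SAP 5.3 (Appendix 3, record consolidation) covers a dose of several vials that was wrongly entered as separate injections. The algorithm starts with "Identify all injection records within 60 minutes of one another". It then applies two retention rules:

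- The surviving record: "Record with earliest injection date/time retained with corresponding contextual information".
- What the others contribute: "Combine/sum values related to the dose (eg, lot numbers, number of vials, volume injected, nominal and actual dose) into the single retained record".

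Merging is barred when the records give clearly conflicting reasons, for example bleeding on one and prophylaxis on the other. A blank is treated differently: "However, if one record has reason or bleed information missing, then consolidation can be performed".

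The same appendix has a rule for removing true duplicates. Those records must agree on time, bleed information, lot and vials. It makes one allowance: "However, if one reason is missing, then they can be considered duplicates and removed". It does not say which record is kept.

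On counting, SAP 4.4.1.1 states: "A bleeding episode is counted in the analysis if it was treated with BIVV001". It adds: "Bleeding episodes of an unknown type will be included in the determination of the annualized bleeding rate".

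**The concern.** The SAP foresees a pair in which one record has no reason or bleed information, and it permits the merge. It does not then say that the information present on the other record is carried over. The only retention rule for non-dose fields points to the earliest record. If that is the blank record, a literal program keeps the blank and discards what the caregiver entered on the second vial.

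This matters because the diary marks an injection as bleed treatment through the reason for dosing (Protocol 8.1.1), and the treated ABR counts bleeds treated with BIVV001. An injection left without a reason has no route into the treated ABR, the annualized joint bleeding rate (AJBR), ABR by type and location, or the summaries of injections and dose per bleed.

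**Working it through.** The documents give no figure to reproduce, so the check applies the rules to an example and then sizes one lost bleed.

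**1. Literal application.** Assumed example: one bleed, two vials (500 IU and 250 IU) entered 10 minutes apart, and no other bleed injection for that episode. ABR = treated bleeds / efficacy days × 365.25 (SAP 4.4.1.1). A full year is taken as 52 × 7 = 364 days. A child in the PK subgroup loses the first 7 days: 364 − 7 = 357.

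| Which record has the blank reason | Rule | Merged record | Treated bleeds | ABR, 364 days | ABR, 357 days |
|---|---|---|---|---|---|
| Earlier | Literal SAP | 750 IU, reason blank | 0 | 0 | 0 |
| Earlier | Non-missing reason carried over | 750 IU, bleed | 1 | 1.003 | 1.023 |
| Later | Either | 750 IU, bleed | 1 | 1.003 | 1.023 |

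The loss therefore needs a blank reason on the earlier record.

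**2. Reason present, other bleed fields blank on the earlier record.** The bleed stays in the ABR, because SAP 4.4.1.1 counts bleeds of unknown type. With a blank type it leaves the spontaneous and traumatic rows. With a blank location it can leave the AJBR and the location rows. Location also decides whether injections up to 72 hours apart form one episode, and the SAP does not say how a blank location is linked.

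**3. Size of one lost bleed.** Drop in mean ABR = (365.25 / 364) / N = 1.0034 / N.

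- N = 65 (planned enrolment): 0.0154
- N = 50 (planned completers): 0.020
- N = 25 (one age cohort): 0.040

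With equal follow-up, the relative loss is lost bleeds divided by total bleeds. Over an assumed 60 participant-years and an assumed ABR of 0.5, 1 or 2 (30, 60 or 120 bleeds), one lost bleed is 3.3%, 1.7% or 0.8%.

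For the planned negative-binomial model, one data set was simulated: 65 children, 364 days each, 78 bleeds. Total time is 65 × 364 / 365.25 = 64.78 years.

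- All bleeds kept: 78 / 64.78 = 1.204 (95% CI 0.887 to 1.635)
- Three bleeds lost: 75 / 64.78 = 1.158 (0.842 to 1.593)

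**4. Are multi-vial doses common enough to matter?** Vials are 250, 500, 1000 and 2000 IU (Protocol Table 5). Bleed doses use nominal strength rounded up to whole vials (Protocol 6.1.6.2). At 50 IU/kg, rounding up to the next 250 IU and using the fewest vials:

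- 12 kg: 600 → 750 IU, 2 vials
- 15 kg: 750 IU, 2 vials
- 25 kg: 1250 IU, 2 vials
- 30 kg: 1500 IU, 2 vials
- 35 kg: 1750 IU, 3 vials
- 10, 18, 20 and 40 kg: 1 vial each

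Split entries are plausible across much of the weight range. How often the first of them lacks a reason is not stated.

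**5. Ties and duplicates.** In two of the four consolidation scenarios the injection times are identical, so no record is earliest and the rule gives no answer. For true duplicates the bleed information must already match, so only the reason label is undetermined.

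**The case against.** The strongest reply is that the appendix already limits what may be done to diary data: "Only changes defined as not requiring participant confirmation and that are supported by site source documentation will be allowed". Erasing a recorded bleed is hard to fit within that limit, and the merge is permitted rather than required. The diary also prompts for reason, type and location, and investigators review bleed data at visits and calls (Protocol 8.1.1, 8.1.2). A sensible programmer might carry the value over unasked. These points make a silent loss less likely, but none says which field value survives an automated merge, so the gap stands.

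A reader might infer more than the documents support:

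- *Every merged pair with a blank loses a bleed.* No. The reason itself must be blank, on the earlier record, with no other bleed injection for that episode outside the 60-minute window.
- *The error can only lower the bleed count.* That is true of the reason field alone. A retained bleed with a blank location might fail to link to a follow-up injection at a named joint, so one episode could be counted as two.
- *The duplicate rule has the same defect.* It relaxes only the reason. Where bleed information applies it must match, so whichever record is kept still holds it.
- *The ABR could fall by 10%.* That is three losses out of 30 bleeds. Both the three and the 30 are assumptions.

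**Conclusion.** The point holds for record consolidation. Read together, the retention rule and the permission to merge blanks give a wrong result when the earlier record has no reason and the later one is marked as a bleed. When only type or location is blank, the harm is confined to the AJBR, the type/location tables and the 72-hour linkage.

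The total effect cannot be computed and is probably small: per lost bleed, about 0.015 on the overall mean ABR (65 children) or 0.04 in a 25-child cohort. This assumes 364 efficacy days each and that bleed information sits on the injection record, as the duplicate rule implies. In the simulated example, three losses moved the estimate well within its confidence interval. The primary endpoint, inhibitor development, is untouched, and the ABR is a descriptive secondary endpoint. The point still merits correction, because a prespecified algorithm should not let a blank override a recorded bleed.

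**What to change.** In SAP 5.3, record consolidation, keep the earliest date and time, but take reason, bleed type, location and sublocation from whichever merged record has a non-missing value. State that this also applies when times are identical and no record is earliest. For true duplicates, keep the record with the non-missing reason. A listing of all merged records that had a blank field would let the effect be seen.

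The cost is a sentence or two and a small programming change, with no new data. It should be settled before database lock, so that in this open-label study the choice is not made with the bleed results in view.
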